## 19.2. Schedule of Assessments

Table 3: Schedule of Assessments

Study Interval	Baseline Screening	Vector (AVXS-101) Injection (Inpatient)		Follow-up (Outpatient)										Notes	
Study Day	-60 to -2	-1	1	2-3	7	14	21	30	44	60	72	Monthly Through M12 	M15/ EOS		
Window					± 2								± 7		
Informed Consent	X														
Spinal X-ray	X														
Demographics/ Medical History	X		X	(X)	X	X	X	X		X		X	X	Medical history collected at baseline; review of systems conducted at each study visit. (X): Patients to remain inpatient 48 hours post-dose for observation and AE monitoring.	
Physical Exam	(X)		X	X	X	X	X	X		X		X	X	Includes measuring head circumference. (X): Baseline procedure must be completed within 30 days of dosing.	
Vitals/Weight/ Length/Height	(X)		X	X	X	X	X	X		X		X	X	Vital signs will include BP, respiratory rate, pulse, and axillary temperature. Vitals including BP, respiratory rate, pulse axillary temperature, pulse oximetry and HR will be monitored and recorded every 15 minutes (± 5 minutes) from dosing for four hours and every hour (± 15 minutes) for 24 hours following the AVXS-101 dosing procedure. (X): Baseline procedure must be completed within 30 days of dosing.	
Pulse Oximetry	(X)		X	X	X	X	X	X		X		X	X	(X): Baseline procedure must be completed within 30 days of dosing.	
Pulmonary Exam	(X)							X		X		X	X		

 Patients who reached the Month 12 visit prior to Protocol Amendment 7 had their EOS assessments conducted at Month 12.

Study Interval	Baseline Screening	Vector (AVXS-101) Injection (Inpatient)		Follow-up (Outpatient)										Notes
		-1	1	2-3	7	14	21	30	44	60	72	Monthly Through M12 	M15/ EOS	
Study Day	-60 to -2													
Window								± 2					± 7	
12-Lead ECG	X		X	X								(X)	X	Irrespective of study schedule, after signing the updated informed consent, all patients enrolled prior to the Amendment 5 version of the protocol should have ECG, 24-hour Holter monitoring, and echocardiogram done at the next scheduled visit and then in conformity with the study SoA. (X): Months 3, 6, 9, and 12 visits.
12-Lead Holter Monitor	X	X	X	X				X		(X)		(X)	X	ECGs extracted from Holter by central reader in triplicate at the following time points: pre-dose, 2h, 4h, 6h, 8h, 12h, 24h, 36h, and 48h during the patient's inpatient stay. (X): Months 2, 3, 6, 9, and 12 visits.
Echocardiogram	X											(X)	X	Irrespective of study schedule, after signing the updated informed consent, all patients enrolled prior to the Amendment 5 version of the protocol should have echocardiogram done at the next scheduled visit and then in conformity with the study SoA. (X): Months 3, 6, 9, and 12 visits.
Capillary Blood Gas		X		(X)										(X): Laboratory samples collected on Day 2.
HFMS- Expanded (with video)	(X)							X				X	X	Will be conducted for patients ≥ 24 months of age; patients < 24 months of age at study entry will begin HFMS-E at such time that 24 months of age is reached. (X): Baseline procedure must be completed within 30 days of dosing.
Bayley III (with video)	(X)							X		X		X	X	Gross and fine motor sections will be performed at screening and monthly through 15 months. (X): Baseline procedure must be completed within 30 days of dosing.

Study Interval	Baseline Screening	Vector (AVXS-101) Injection (Inpatient)		Follow-up (Outpatient)										Notes	
		-60 to -2	-1	1	2-3	7	14	21	30	44	60	72	Monthly Through M12 †	M15/ EOS	
Study Day	Window	± 2												± 7	
Motor Milestone Development Survey (with video)	(X)								X		X			X	X
Hematology / Chemistry	(X)	(X) *		(X) §	X	X	X	X	(X) †	X	(X) †		X	X	(X): Baseline procedure must be completed within 30 days of dosing. (X)*: Laboratory samples collected prior to dosing are to be processed locally. (X) § : Laboratory samples collected on Day 2. (X) † : Liver function test (AST, ALT, total bilirubin, alkaline phosphatase, GGT) only.
Coagulation	(X)	(X) *		(X) §	X	X	X	X		X			X	X	
Urinalysis	(X)	(X) *		(X) §	X	X	X	X		X			X	X	
CK-MB	X				X			X		X			(X)	X	Troponin I will be measured instead of CK-MB in new patients who are screened and enrolled after amendment 5 (protocol version 6.0) goes into effect. Participants who have been screened and enrolled but who have not yet received gene replacement therapy (visit #2) at the time that amendment 5 (protocol version 6.0) goes into effect will have baseline troponin I testing prior to treatment with AVXS-101, and will have troponin I testing in place of CK-MB. CK-MB will be collected from all other participants. (X): Months 2, 6, 9, and 12 visits.
Troponin I	X				X			X		X			(X)	X	
Virus Serology	(X)														(X): Baseline procedure must be completed within 30 days of dosing.
Blood for diagnostic confirmation testing	X														To be performed by central laboratory.

Study Interval	Baseline Screening	Vector (AVXS-101) Injection (Inpatient)		Follow-up (Outpatient)										Notes
		-1	1	2-3	7	14	21	30	44	60	72	Monthly Through M12 T	M15/ EOS	
Study Day	-60 to -2													
Window								± 2					± 7	
Saliva, Urine, and Stool Samples (for viral shedding)		X			(X)	(X)	(X)	(X)						(X): Sites participating in the viral shedding sub-study will collect 24-hour full volume samples for urine and feces through 24 and 48 hours. All other sites will collect singular urine and feces samples within 24 hours and 48 hours of dosing. Full urine and feces samples will be collected for patients ≥ 48 months who are no longer in diapers.
Baseline Screening of Biological Mother (Anti-AAV9 Ab)	(X)													Serum sample collected at screening for anti-AAV9 antibodies. (X): Baseline procedure must be completed within 30 days of dosing. (X)*: Additional sampling may be performed at subsequent time points if ELISpot value(s) continue to be elevated, based on further discussion with the PI and Medical Monitor.
Immunology Labs (Anti-AAV9/SMN)	(X)				X	X	X	(X)						(X): Additional sampling may be performed at subsequent time points if ELISpot value(s) continue to be elevated, based on further discussion with the PI and Medical Monitor.
Immunology Labs (IFN-γ T-cells)					X	X	X	(X)						(X): Additional sampling may be performed at subsequent time points if ELISpot value(s) continue to be elevated, based on further discussion with the PI and Medical Monitor.
Prophylactic Prednisolone		X	X	X	X	X	X	X	X	X	X			See Section 9.2.1. Daily dosing from 24 hours prior to scheduled AVXS-101 dose and continued as per protocol.
Study Product Administration with fluoroscopic / radiographic guidance			X											
Photograph Injection Site			X		X	X	X	X						
Adverse Events	X	X	X	X	X	X	X	X		X		X	X	

Study Interval	Baseline Screening	Vector (AVXS-101) Injection (Inpatient)		Follow-up (Outpatient)										Notes
		-1	1	2-3	7	14	21	30	44	60	72	Monthly Through M12 T	M15/ EOS	
Study Day	-60 to -2													
Window								± 2					± 7	
Prior and Concomitant Medications	To be collected from 2 weeks before study dosing until final study visit													

AE = adverse event; ALT = alanine aminotransferase; AST = aspartate aminotransferase; CK-MB = Creatinine kinase-MB (isozyme MB); ECG = electrocardiogram; ELISpot = enzyme-linked ImmunoSpot; GGT = gamma glutamyl transferase; IFN-γ = interferon gamma; PI = Principal Investigator; SoA = Schedule of Assessments;

### 19.3. Summary of Changes

The section below highlights content changes represented in version 5.0 of the SAP.

Global updates made throughout the entire document and not specified in the list of section-specific changes below:

Minor wording and formatting updates have been made throughout the SAP in order to correct typographical errors and to align wording across sections. These changes did not change the intent of the analysis.

Protocol Amendments 5 and 6 introduced the potential for patients to be dosed with Dose C. The addition of Dose C to the study meant that the previous wording used throughout the SAP of

“AVXS-101 at the optimal dose” was no longer relevant. This wording has been removed throughout and, in its place, clarifying text has been added to document the plan for comparing both Dose B and Dose C (separately) to PNCR database, as well as comparing Dose B and Dose C combined to the PNCR database.

The approval signature page was updated to remove [REDACTED] as Clinical Operations signatory and to add [REDACTED] as Clinical Operations signatory.

Section 2.1 was updated to remove [REDACTED] as the responsible CRO for statistical and programming support.

Section 2.2.1 was updated to detail when the primary analyses for efficacy and safety would be conducted; and to detail that an additional analysis of efficacy and safety data would be conducted once the last Cohort 2 patient has completed the 12 month visit.

Section 3.5 was updated to include details regarding Dose C, including the additional clinic visits for Dose C patients on Days 44 and 72.

Section 3.7 was updated to include details regarding Dose C.

Section 3.10 was updated to reflect an updated version of the study flowchart (Figure 1). The schedule of study assessments was moved to Appendix 22.3.

Section 4.8.1.3 was updated to include measurement of head circumference.

Section 4.8.1.4 was updated to reflect the timepoints for ECG assessment.

Section 4.8.1.5 was updated to reflect the timepoints for echocardiogram assessment.

Section 4.8.1.6 was added to provide the details of 24-hour Holter monitoring.

Section 5 was updated to expand the definition of the Enrolled Set to be based on patients who received an injection of AVXS-101.

Section 5.4.2 was added to document the definition of the Per Protocol Analysis Set.

Section 5.5 was updated to clarify the PNCR control group for the older patient cohort consisted of 15 patients, not 12 patients; to clarify that the PNCR control group for the younger cohort may have demonstrated the milestones of interest at any point, not at or before turning 36 months of age; to include the sensitivity analysis for the older patient cohort using a different group of 15 PNCR patients.

Section 6.1 was updated to state that no adjustments for multiple comparisons would be made.

Section 6.5 was updated to define the visit windows for Cohort 3 patients, and to include rules for remapping of efficacy data for PNCR patients which have data missing at the Baseline visit.

Section 7.1 was updated to include a summary table for patients who discontinued due to AE, and to clarify that a listing of major protocol deviations would be produced; to indicate that the number (%) of patients in the PP Set would be summarized.

Section 7.2 was updated to clarify which demographic characteristics would be summarized for the PNCR populations.

Section 7.3 was updated to indicate the table of SMA medical history should be based on the FAS.

Section 7.4.2 was updated to include a listing of AEs for patients who did not follow the protocol-prescribed taper for prednisolone.

Section 8.1.1 was updated to remove the sample SAS code; to clarify that patients in the PNCR group who achieved the milestone at either the Baseline visit or at a post-Baseline visit within 12 months of Baseline would be considered to have met the milestone; to indicate that the analysis of the primary endpoint will be repeated using the PP Set as a sensitivity analysis.

Section 8.1.2 was updated to remove the sample SAS code, and to include a sensitivity analysis based on the Sensitivity PNCR group; to indicate that the analysis of the primary endpoint will be repeated using the PP Set as a sensitivity analysis.

Section 8.2.1 was updated to remove the reference to sample SAS code; to include a sensitivity analysis based on the Sensitivity PNCR group; to clarify that patients in the PNCR group who achieved the milestone at either the Baseline visit or at a post-Baseline visit within 12 months of Baseline would be considered to have met the milestone.

Section 8.3.1 was updated to remove the sample SAS code; the text related to the comparison to PNCR data for this endpoint was removed as Bayley Scale scores are not available in the PNCR dataset.

Section 8.3.2 was updated to state the summary would be based on descriptive statistics only; to state that change from baseline at each visit and maximum change from baseline will be summarized.

Section 8.4 was updated to include details regarding a sensitivity analysis for patients aged  $\geq 24$  and  $< 60$  months at time of dosing.

Sections 8.4.1, 8.4.2, and 8.4.3 were added to describe additional sensitivity analyses based on HFMSE.

Section 11.1 was updated to include details regarding Dose C and to include the derivation for duration of injection; text was added to state that duration of injection would not be calculated if either the start or stop time of the injection was missing.

Section 11.3.2.2 was updated to include 3 additional AE tables needed for CT.gov reporting purposes: incidence of serious TEAEs by relationship, incidence of TEAEs leading to death by relationship, incidence of non-serious TEAEs.

Section 11.3.2.4 was updated to detail the full set of AEs of special interest for the AVXS-101 program.

Section 11.4.1 was updated to include CK-MB and Troponin I as chemistry parameters assessed for this study; to remove the tables of PCS values for labs as this will be maintained outside of the SAP.

Section 11.4.2 was updated to clarify that urinalysis data would only be presented in listings; text was added to clarify that the listing of PCS laboratory values would include all of the results for only the parameter(s) meeting PCS criteria; to clarify how elevated LFTs would be summarized.

Section 11.5 (Table 11) was removed as definitions for PCS values are maintained outside of the SAP.

Section 11.6 was updated to reflect the full set of timepoints for ECG assessment; to add a statement to indicate that definitions for PCS values are maintained outside of the SAP.

Section 11.7 was updated to reflect the full set of timepoints for 24-hour Holter monitoring.

Section 11.8 was updated to include a table summarizing head circumference data.

Section 11.9 was updated to reflect the full set of timepoints for echocardiogram assessment.

Section 11.2 was updated to refer to Vector Shedding instead of Viral Shedding.

Section 13 was updated to include details regarding Cohort 3.

Section 16 was updated to remove [REDACTED] as the responsible CRO for statistical and programming support.

The section below highlights content changes represented in version 6.0 of the SAP.

Text was updated throughout the SAP to indicate that no formal statistical comparisons would be made for Dose C (alone) to PNCR, and that no summaries of data would be produced for Dose B+C combined.

Text was added throughout to define COVID-related analyses to be conducted in necessary.

Text was updated throughout to clarify that summaries of data would only be produced for the ECAS in instances where the ECAS reflects a subset of the ITT Set.

Section 5 was updated to include the definition of the Screened Set.

Section 5.5.2 was updated to clarify the definition of the PP Set.

Section 5.4.1 was updated to clarify the end of study visit could occur remotely or at the study site.

Section 7.1 was updated to include a separate listing which summarizes all protocol deviations related to COVID-19; to clarify how completed patients are defined; and to add a summary of completions within and outside of a 30-day window of the last study visit.

Sections 11.1 and 11.2 were updated to clarify the calculation of planned volume to be administered and treatment compliance. Section 11.1 was updated to state duration of injection is expressed in seconds, rather than minutes.

Section 11.3 was updated to include serious TEAEs related to study treatment in the AE overview table.

Section 11.3.2.4 was updated to reflect the updated approach to identifying AESIs.

Section 11.4.2 was updated to reflect the updated approach to identifying elevated liver function tests.

Section 11.5 was updated to clarify that for body weight, the PCS criteria are based on percentile weights for age and sex as defined by the World Health Organization Child Growth Standards.

These definitions extend through 60 months of age. If a patient is >60 months of age at the time of their weight assessment, they will not be assessed for PCS weight values.

The appendices of proposed lists of tables, listings, and figures were removed.

Appendix 22.2 (Lot Titers) was removed because this information is being maintained outside of the SAP.

Final

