The primary efficacy endpoint for the group of patients  $\geq 6$  months and  $< 24$  months of age at time of dosing will be the proportion of treated patients who achieve the ability to stand without support up to the 12-month study visit. Twelve children aged  $\geq 6$  months and  $< 24$  months will be enrolled who receive Dose B. The proportion of patients developing the ability to stand without support will be compared with a cohort of eligibility-matched patients from the PNCR natural history study of SMA. Based upon a review of eligibility-matched patients from the PNCR, 14% of patients who meet the study criteria for patients  $\geq 6$  months and  $< 24$  months of age achieved the ability to stand without support, and 10% achieved the ability to walk without assistance. We expect 85% of treated patients  $\geq 6$  months and  $< 24$  months of age to achieve the ability to stand alone and 60% to achieve the ability to walk without support. With this efficacy a sample size of 12 patients would provide power of  $> 90\%$  to detect a significant difference compared with the matched control cohort with  $\alpha = 0.05$  using a two-sample 2-sided superiority Fisher exact test.

The primary efficacy endpoint will be the change in HFMSE in treated patients between 24 months and  $< 60$  months of age at time of dosing. Twelve children aged  $\geq 24$  months and  $< 60$  months will be enrolled. Change in HFMSE score at 12 months will be compared with a cohort of eligibility-matched patients from the PNCR natural history study of SMA. Based upon a review of eligibility-matched patients from the PNCR, a mean change of -1.33 points (standard deviation = 4.32 points) is seen at 12 months from baseline among patients aged 2-5 years at first evaluation with 3 copies of *SMN2* in the PNCR dataset. We expect to observe a mean increase

of 8 points from baseline on the HFMSE with equivalent variance. Based upon these assumptions, 12 patients between 24 and <60 months at enrollment will have >90% power to detect a significant difference with  $\alpha = 0.05$  when compared to patient-level data available from the PNCR dataset using two-sample ANOVA.

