## 1.1. Key Definitions

Term	Definition
AE	Adverse Event (AE): Any untoward medical occurrence in a clinical investigation patient which does not necessarily have a causal relationship with the drug or device under study.
Age	For a given event, age will be expressed in months and rounded to one decimal place. A month is standardized to a period of 30 days. Age at event = (date of event – date of birth +1) / 30.  Age at Baseline will be defined/displayed in months. Age at Baseline = (first dose date – date of birth +1)/30.
Baseline	Baseline, unless otherwise specified in the Statistical Analysis Plan (SAP) sections, refers to the last measurement or evaluation made prior to the injection of AVXS-101.
First Dose Date	The first dose date, study day 1, will be the date of administration of the first dose of study drug after enrollment.
MedDRA	Medical Dictionary for Regulatory Activities (MedDRA) is a medical terminology used to classify adverse event information associated with the use of biopharmaceuticals and other medical products.
Study Day	First dose of study medication will be administered on study day 1. There is no study day 0. If the event happened on or after the first dose date, study day is defined as event date – first dose date + 1. If the event happened prior to the first dose date, study day is defined as event date – first dose date.

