### 2.2. Timings of Analyses

#### 2.2.1. Primary Safety and Efficacy Analysis

Patients from Cohort 1 and Cohort 2 will be followed for a total of 12 months post-dose; patients from Cohort 3 will be followed for a total of 15 months post-dose. The primary analyses for efficacy will be assessed when all patients have completed 12 months of follow-up study visits following AVXS-101 administration, and the primary analyses for safety will be assessed when the last patient of Cohort 3 reaches 15 months post-dose (and database lock will take place after the last patient reaches 15 months post-dose).

On 18-November-2021, AveXis made the decision to terminate the study early. As a result, Cohort 3 did not enroll the full number of planned patients. Per the protocol, a total of 24 patients were planned to be enrolled into Cohort 3: 12 patients aged > 6 months and < 24 months and 12 patients aged  $\geq$  24 and < 60 months. When the decision was made to terminate the study early, a total of 4 patients aged > 6 months and < 24 months had been enrolled and treated in Cohort 3. Because of the early study termination, the majority of analyses pre-specified in the protocol to be conducted on patients in Cohort 3 are no longer applicable. Unless otherwise specified, the data collected for patients in Cohort 3 will be summarized using descriptive statistics and summarized in data listings.

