## 11.5. Vital Signs

Vital signs will include blood pressure, respiratory rate, pulse, heart rate, pulse oximetry and axillary temperature. Body weight and length and/or height will also be collected.

Vital signs will be examined at each scheduled visit and time point. The baseline value will be the last measurement before date and time of the injection of study drug. Mean changes from baseline to each post-baseline visit and time point will be summarized with the baseline mean, visit/time point mean, change from baseline mean, standard deviation, minimum, maximum, and median. Summaries will be presented overall and by actual dose received and age group.

In addition, vital signs results will be flagged as PCS if they meet the pre-specified criteria which are defined outside of this SAP. The number and percent of patients meeting each PCS criterion at each scheduled visit and time point will be summarized overall and by actual dose received and age group. For body weight, the PCS criteria are based on percentile weights for age and sex as defined by the World Health Organization Child Growth Standards. These definitions extend

through 60 months of age. If a patient is >60 months of age at the time of their weight assessment, they will not be assessed for PCS weight values.

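### The weight safety flag in SAP 11.5 stops at 60 months of age, so children dosed after about 48 months lose it before Month 12

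*SAP*

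**What the plan says.** SAP 11.5 plans PCS flags for vital signs and body weight: "vital signs results will be flagged as PCS if they meet the pre-specified criteria which are defined outside of this SAP". For weight, "the PCS criteria are based on percentile weights for age and sex", taken from the WHO growth standards, which the SAP says extend through 60 months. Beyond that age the rule is: "If a patient is >60 months of age at the time of their weight assessment, they will not be assessed for PCS weight values". The sentence setting this limit is the same in the operative text of 11.5 and in the version 6.0 change log (19.3), so there is no conflict between them.

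The output is a table by visit, overall and by dose and age group: "The number and percent of patients meeting each PCS criterion at each scheduled visit and time point will be summarized". Separately, 11.5 plans mean change from baseline for vital signs, with no age limit.

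On age and follow-up, Protocol 8.1 admits children up to and including 60 months, given as 1800 days. SAP 1.1 fixes the unit: "A month is standardized to a period of 30 days". SAP 2.2.1 states "Patients from Cohort 1 and Cohort 2 will be followed for a total of 12 months post-dose", and SAP 7.1 places Month 12 at Day 360.

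**The concern.** The entry limit and the end of the weight criterion are the same age, but follow-up runs for another year. A child dosed shortly before 60 months has almost no post-dose visit at which weight can be flagged. Those who drop out of the table are always the oldest children in the older group, and their number grows at each visit.

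The plan itself treats low weight-for-age as important: Protocol 8.2 excludes children below the WHO 3rd percentile. A later fall below that level would be a new finding after entry, in children who all receive prednisolone (Protocol 9.2.1). Mean change in raw weight does not replace the flag. Growing children gain weight, so a group mean can rise while one child falls below the percentile for his or her age.

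**Working it through.** The plan gives no figure for the share of children left unassessed, so there is none to reproduce.

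**Inputs**
- Older group: planned size 12, age at dosing 24 to <60 months, a width of 36 months (Protocol 14.4: "12 patients between 24 and <60 months at enrollment will have >90% power").
- End of the flag: 60 months, or 60 × 30 = 1800 days (SAP 11.5 and 1.1).
- Last visit: Month 12, Day 360 (SAP 7.1).
- Ages at dosing: not in the documents. An even spread over 24 to 60 months is an assumption.

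**Age at dosing beyond which the flag is lost by Month 12**
- Round months: 60 − 12 = 48.
- SAP age formula: Day 360 is 359 days after dosing, which adds 359/30 = 11.97 months. The threshold is 60 − 11.97 = 48.03 months.

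**Share of the older group unassessed, even spread**
- Month 12: (60 − 48)/(60 − 24) = 12/36 = 33.3%, or 4 of 12. With the SAP age formula it is 11.97/36 = 33.2%.
- Visit at Day 353 to 367 (±7 days): 32.6% to 33.9%.
- Calendar months of 30.44 days in place of 30-day months: 30.8% to 32.8%.
- Month 6: 6/36 = 16.7%, or 2 of 12.
- All monthly visits: the share at month m is m/36, so the average over Months 1 to 12 is (1 + 2 + … + 12)/(12 × 36) = 78/432 = 18.1%.

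**If ages are not evenly spread (Month 12)**
- Leaning young (triangular density on 24 to 60, peak at 24): (12/36)² = 11.1%.
- Leaning old (peak at 60): 1 − (24/36)² = 55.6%.
- In principle the share could lie anywhere from 0 to 100%.

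**Where the loss falls**
A child dosed before 24 months and followed for at most 15 months stays below 24 + 15 = 39 months, so the younger group loses nothing. Cohort 1 enrolled only younger children, and the 4 patients treated in Cohort 3 were all in the younger group (SAP 2.2.1). The whole loss is therefore in the older Dose B group.

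**The case against.** The strongest reply is that this is a disclosed scope limit and not an error. SAP 11.5 states the rule and its reason. The exclusion depends on age, not on the weight result. Weight is an additional safety endpoint with descriptive statistics only (SAP 4.8.1.2), and the primary safety endpoints are adverse events (SAP 4.4). Weights are still collected, change from baseline continues, and the adverse event tables and physical examination shift tables have no such cut. The PCS thresholds sit in an external document, so the direction and percentile of the weight criterion cannot be checked. All of this stands and keeps the point minor. It does not supply an age-specific flag for the children concerned.

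Two stronger readings are tempting, and the documents support neither.

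- **Diluted percentages.** SAP 6.1 puts safety tables on all injected patients, and 11.5 states no denominator. A reader might infer that unassessed children count as unflagged and pull the percentage down at later visits. But SAP 6.3 analyses patients with non-missing values, and an unassessed child has no PCS value. Nothing prescribes the diluted calculation; the denominator is only left unstated in 11.5.
- **Carrying the 60-month cut-off forward.** A reader might infer that the 60-month value is a safe low-weight flag for older children. The SAP applies no cut-off after 60 months and does not say this. If percentile weights rise with age, a fixed cut-off gives no false low flags, but it misses children who lie between it and the cut-off for their own age, and counts them as assessed and unflagged. As an illustration, take the 3rd percentile, normally distributed weights, a cut-off rising by g kg per year and t years past 60 months. Sensitivity is Φ(z₀.₀₃ − g·t/SD)/0.03. With g of 1 to 2 kg per year and SD of 2 to 3 kg (assumed; neither is in the documents), this gives about 7% to 45% at 72 months and 37% to 69% averaged over 60 to 72 months. For a safety flag, that errs in the wrong direction.

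**Conclusion.** The point holds as a minor gap in a safety output. By the plan's own limits, children dosed after about 48 months leave the weight flag before their last visit, and nothing replaces it. Under an even age spread, about a third of the older group (4 of 12) is unassessed at Month 12 and about 18% of its monthly weight assessments are unflagged. The Month 12 share runs from about 11% to 56% under the two uneven spreads tried. These figures rest on the assumed ages and the planned group size. SAP version 6.0 is dated 22 November 2021, after the analysis that followed the last Cohort 2 patient's Month 12 visit (SAP 2.2.2), so the sponsor holds the birth and dosing dates and can give the exact count. Weight data as such are not lost; only the age-specific flag is.

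**What to change.** In SAP 11.5 and in the external PCS criteria:

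1. Replace the exclusion above 60 months with a named weight-for-age reference that covers the ages reached in follow-up. A child dosed at 60 months and followed for 12 reaches about 72 months.
2. Show the number of children assessed for PCS weight at each visit, by dose and age group, and use it as the denominator of the percentage.
3. Identify each flag by the reference used, because the reference changes at 60 months and a child's status could shift at the join.

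The cost is a short text edit, the same change in the external criteria and a small programming change. No new data are needed. The one drawback is the change of reference at 60 months, which item 3 makes visible.
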